8.0 Eligibility Screening

8.1 *Describe screening procedures for determining subjects' eligibility. Screening refers to determining if prospective participants meet inclusion and exclusion criteria.*

Include all relevant screening documents with your submission (e.g. screening protocol, script, questionnaire).

Response: We will first look at the electronic medical record of our clinics to identify potential candidates and this will be followed by patient doctor interaction at the time of their visit. Potential candidates will be scheduled to come to the research unit for a screening visit. Please see the screening documents

N/A: There is no screening as part of this protocol.

9.0 Recruitment Methods

N/A: This is a records review only, and subjects will not be recruited.

NOTE: If you select this option, please make sure that all records review procedures and inclusion/exclusion screening are adequately described in other sections.

9.1 *Describe when, where, and how potential subjects will be recruited.*

NOTE: Recruitment refers to how you are identifying potential participants and introducing them to the study. Include specific methods you will use (e.g. searching charts for specific ICD code numbers, Research Participant Groups, posted advertisements, etc.).

Response:

Participants will be identified by prescreening clinical charts prior to their clinic visit, and patient doctor interaction at the time of their visit at the Diabetes Endocrinology Center of WNY and Western New York VA Hospital. If the patient expresses interest after speaking with their physician and provide their contact information, they will be scheduled for a screening visit. The recruitment will start immediately after approval by IRB. Advertisements and flyers will be posted at these locations with the contact phone number for the patient to call the research team, if interested in participating.

Locations include:

1. [name]
2. [name]

3. [name]

4. [name]

9.2 *Describe how you will protect the privacy interests of prospective subjects during the recruitment process.*

NOTE: Privacy refers to an individual's right to control access to him or herself.

Response: HIPAA waiver is being requested, so that we will be able to use identifiable health information for subject recruitment. Any potential participant's personal health information will be kept solely between the study team and handled just as clinic patients' personal health information is handled. Locked file cabinets in locked offices for written data, password protected logins for electronic data, private rooms for any patient discussion. The data will only be shared with the study team who have all taken CITI training and will follow University privacy policies. We will not retain personal identifiers once the candidate is identified in the electronic medical record and contacted, no matter if the candidate agrees or declines to participate.

9.3 *Identify any materials that will be used to recruit subjects.*

NOTE: Examples include scripts for telephone calls, in person announcements / presentations, email invitations.

 *For advertisements, include the final copy of printed advertisements with your submission. When advertisements are taped for broadcast, attach the final audio/video tape. NOTE: You may submit the wording of the advertisement prior to taping to ensure there will be no IRB-required revisions, provided the IRB also reviews and approves the final version.*

Response: Please see attached document

10.0 Procedures Involved

10.1 *Provide a description of all research procedures or activities being performed and when they are performed once a subject is screened and determined to be eligible. Provide as much detail as possible.*

NOTE: This should serve as a blueprint for your study and include enough detail so that another investigator could pick up your protocol and replicate the research. For studies that have multiple or complex visits or procedures, consider the addition of a schedule of events table in in your response.

Screening Day

All subjects will have completed the following procedures prior to participating in the study:

- 1) Informed consent
- 2) Medical history
- 3) Physical exam (including body mass index measurement)

We will collect general demographic data regarding years of education, race/ethnicity.

A continuous glucose monitor will be calibrated with finger blood glucose result and the probe of the monitor will be inserted into the abdominal subcutaneous tissue. Patient will be instructed on how to use continuous glucose monitor, they will be instructed to wear it and document the time and the types of food of every meal for at least 72 hours after the screening visit.

Subjects will be instructed not to change their medications during the whole study period and not to take insulin for at least 4 hours before visit 1, visit 5 and visit 6.

Visit 1:

Subjects will come back within 2 weeks and will arrive after having fasted overnight (10 hours) at 7 to 7:30 am. They will then be randomized to either active tDCS or sham tDCS with block randomization (block size of 10). We will test urine pregnancy test to rule out pregnancy. Pregnant subject will be excluded from the study. We will also administer the three-factor eating questionnaire (Stunkard and Messick, 1985), which measures eating habits and attitudes toward food, weight and dieting, and a personality questionnaire, the Big Five (Costa and McCrae, 1989). We will evaluate cognitive responses to food with a 20-minute computerized task designed to engage the inhibitory control circuit when confronted with food stimuli, as well as engaging the other two components of executive function: working memory and cognitive flexibility. The task consists of 3 parts: a version of a Go/No-Go (GNG) task modified for food; an N-back memory task with food images, similar to a task used in a previous study; and a combined N-back and GNG task. In the food modified GNG task subjects have to press the space bar of a computer in response to pictures of low-calorie food, refraining from pressing when the pictures are of high-calorie food (25% of the time). In the N-back task, subjects will press the space bar when the picture displayed matches the picture displayed two images before. In the combined task, the subject will press the space bar when a picture of low-calorie food matches the picture displayed two images before, while refraining from pressing when a high-calorie food matches the picture displayed two images before.

Blood sample for BDNF and COMT gene test will be collected. We will also collect blood sample for plasma insulin and glucose level. We will download data from the continuous glucose monitor.

Subjects assigned to active tDCS group will receive 30 min of anodal tDCS delivered with a neuroConnVR DCSTIMULATOR device (neuroConn GmbH, Ilmenau, Germany), at a constant current of 2 mA (with a 30-second ramp at on- and offset) using two sponge electrodes soaked in a sterile 0.9% sodium chloride solution. The anode electrode will be placed over F3 (10–20 EEG system), with the cathode electrode placed over the contralateral supraorbital area, above the right eyebrow. This montage was used in a recent study that showed reduction of body weight and intake of soda and fat in a sample of obese subjects.

Subjects assigned to sham tDCS group will receive 15 seconds of anodal tDCS delivered with a neuroConnVR DCSTIMULATOR device (neuroConn GmbH, Ilmenau, Germany), at a constant current of 2 mA (with a 30-second ramp at on- and offset) using two sponge electrodes soaked in a sterile 0.9% sodium chloride solution. However, they will stay at the research center for 30 minutes with electrodes on their scalp. Before starting the stimulation, a code will need to be entered into the tDCS machine which will decide whether a sham or active stimulation will be performed by the machine automatically in the next 30 minutes. At the beginning of the study, a code that is associated with either active stimulation or sham stimulation will be assigned to the subject based on the randomization. However, neither the subject or the operator of tDCS machine will know what does the code represent.

Visit 2: Subjects will come back next day to receive the second session of the same intervention.

Visit 3: Subjects will come back next day to receive the third session of the same intervention.

Visit 4: Subjects will come back next day to receive the fourth session of the same intervention.

Visit 5: Subjects will fast overnight (10 hours) and come back next morning at 7 to 7:30 AM to receive the fifth session of the same intervention. We will then measure body mass index, plasma insulin and glucose, appetite and cognitive function in response to food. Continuous glucose monitor will be reinstalled, and subjects will be instructed to wear it and document the time and types of food of every meal for at least 72 hours after this visit and 72 hours before the next visit. Subject will be instructed on how to insert and remove continuous glucose monitor again.

Visit 6: Subjects will fast overnight (10 hours) and come back next morning at 7 to 7:30 AM in 4 weeks after visit 5. We will measure body mass index, plasma insulin and glucose, appetite and cognitive function in response to food again. We will download data from the continuous glucose monitor. We will also ask if the subject believed that he/she received active or sham tDCS.

10.2 Describe what data will be collected.

NOTE: For studies with multiple data collection points or long-term follow up, consider the addition of a schedule or table in your response.

Response:

We will collect general demographic data regarding years of education, race/ethnicity. We will also administer the three-factor eating questionnaire (Stunkard and Messick, 1985), which measures eating habits and attitudes toward food, weight and dieting, and a personality questionnaire, the Big Five (Costa and McCrae, 1989).

Plasma glucose and insulin level during screening visit, visit 5 and visit 6

COMT and BDNF gene during screening visit

Weight, height and body mass index (BMI) during screening visit, visit 5 and visit 6
Cognitive response to food during screening visit, visit 5 and visit 6.
Average daily meal counts and type of food based on patient report and continuous glucose meter on visit 1 and visit 6

10.3 *List any instruments or measurement tools used to collect data (e.g. questionnaire, interview guide, validated instrument, data collection form).*

Include copies of these documents with your submission.

Response: Please see form for screening visit, form for follow up visit 1, 2, 5 and 6, eating habit questionnaire, personality questionnaire.

Describe any source records that will be used to collect data about subjects (e.g. school records, electronic medical records).

Response: electronic medical records, clinical charts and research files

10.4 *Indicate whether or not **individual** subject results, such as results of investigational diagnostic tests, genetic tests, or incidental findings will be shared with subjects or others (e.g., the subject's primary care physician) and if so, describe how these will be shared.*

Response: Individual participant lab results will be disclosed to the participant upon their request. If the participant requests documentation be shared with another physician, physician office or hospital, the participant must come to the research center to collect said documentation and/or the documentation can be mailed to their given home address.

10.5 *Indicate whether or not **study** results will be shared with subjects or others, and if so, describe how these will be shared.*

Response: Study results will not be shared directly with subjects. However, study results could be published in the form of a manuscript, to an academic journal.

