1.0 Objectives

1.1 Describe the purpose, specific aims, or objectives of this research.

Response: To study the effects of transcranial direct current stimulation (tDCS) on weight and appetite.

Aim:

- 1. To compare weight loss over one month in active tDCS group with sham tDCS group. We will measure weight of every participants at the beginning of the study and one month after the last session of tDCS*
- 2. To compare change in insulin sensitivity over one month in active tDCS group with sham tDCS group. We will measure fasting insulin and glucose level, and calculate homeostatic model assessment-insulin resistance (HOMA-IR)*
- 3. To compare change in cognitive performance as a response to food over one month in active tDCS group with sham tDCS group. We will evaluate performance in a computerized task that measures executive functions under the presence of food (working memory, inhibitory control and a combination of both). We will assess changes in accuracy and speed in the task under active tDCS versus sham tDCS.*
- 4. To compare change in post-prandial glucose excursion and average meal counts per day. We will use continuous glucose monitor to record the frequency and amplitude of glucose excursion.*

1.2 State the hypotheses to be tested, if applicable.

NOTE: A hypothesis is a specific, testable prediction about what you expect to happen in your study that corresponds with your above listed objectives.

Response:

Hypothesis:

- 1. Active tDCS will result in more weight loss, appetite reduction and improved insulin sensitivity compared with sham tDCS over one month period.*
- 2. The effect of tDCS on weight, appetite, glucose tolerance and cognitive response to food varies according to the underlying allele status of BDNF and COMT gene*

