2.0 Scientific Endpoints

2.1 Describe the scientific endpoint(s), the main result or occurrence under study.

*NOTE: Scientific endpoints are outcomes defined before the study begins to determine whether the objectives of the study have been met and to draw conclusions from the data. Include primary and secondary endpoints. Some example endpoints are: reduction of symptoms, improvement in quality of life, or survival. Your response should **not** be a date.*

Response:

Primary endpoints: change in weight, measured as a percentage of baseline body weight.

Secondary endpoints: change in HOMA-IR, change in average daily meal counts based on frequency of glucose excursion on continuous glucose monitor, change in average amplitude of glucose excursion curve after meals, change in cognitive performance in response to food

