6.0 Inclusion and Exclusion Criteria

6.1 *Describe the criteria that define who will be **included** in your final study sample.*

NOTE: This may be done in bullet point fashion.

Response:

1. Men and women 18 to 80 years of age
2. Body mass index > 30 kg/m²

6.2 *Describe the criteria that define who will be **excluded** from your final study sample.*

NOTE: This may be done in bullet point fashion.

Response:

1. Current participation in any other concurrent clinical trials or previous participation within 30 days before the screening visit
2. Pregnancy or premenopausal women who are trying to be pregnant
3. Patients who are incompetent to give consent
4. Obesity due to a known secondary cause (Cushing's syndrome, hypothyroidism, etc) or a history of weight loss surgery

5. Have taken any of the following medications within the past 3 months:
phentermine, naltrexone, bupropion, topiramate, lorazepam, phendimetrazine, methamphetamine, benzphetamine, diethylpropion

6. Any contraindication to receive transcranial direct current stimulation (tDCS):

- Personal or family history of seizures, epilepsy or other unexplained loss of consciousness.
- Current or past history of skin disease or damaged skin on the scalp at the site of stimulation (i.e. eczema, skin with ingrown hairs, acne, razor nicks, wounds that have not healed, recent scar tissue, broken skin, etc.).
- Prior neurosurgical procedure or radiation.
- Known diagnosis of brain lesions, such as tumor, stroke or multiple sclerosis
- Implanted pacemaker, medication pump, vagal stimulator, deep brain stimulator, Transcutaneous Electrical Nerve Stimulation unit, ventriculo-peritoneal shunt or any metallic implant on the head.

6.3 *Indicate specifically whether you will include any of the following special populations in your study using the checkboxes below.*

NOTE: Members of special populations may not be targeted for enrollment in your study unless you indicate this in your inclusion criteria.

Response:

- Adults unable to consent
- Individuals who are not yet adults (infants, children, teenagers)
- Pregnant women
- Prisoners

6.4 *Indicate whether you will include non-English speaking individuals in your study. Provide justification if you will exclude non-English speaking individuals.*

In order to meet one of the primary ethical principles of equitable selection of subjects, non-English speaking individuals may not be routinely excluded from research as a matter of convenience.

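### Insulin users can enrol, yet section 17.1 analyses HOMA-IR in all subjects without regard to insulin use, so part of this secondary endpoint may not measure insulin sensitivity

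*Combined protocol and SAP*

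**What the plan says.** **Eligibility.** Section 6.1 asks only for age 18 to 80 and BMI above 30. The drug exclusion in section 6.2 ("Have taken any of the following medications within the past 3 months") names nine agents; insulin is not among them, and diabetes is not excluded. Section 9.1 recruits through "patient doctor interaction at the time of their visit at the Diabetes Endocrinology Center of WNY and Western New York VA Hospital". Section 10.1 tells subjects "not to take insulin for at least 4 hours before visit 1, visit 5 and visit 6", an instruction with no purpose unless insulin users may take part. It also says: "Subjects will be instructed not to change their medications during the whole study period".

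**Endpoint.** Section 2.1 lists "Secondary endpoints: change in HOMA-IR" first among the secondary endpoints. Aim 2 calculates it from fasting insulin and glucose and treats it as the measure of insulin sensitivity, which is part of Hypothesis 1.

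**Analysis.** Section 17.1 applies a generalized linear mixed model to HOMA-IR and names no subset. The predictors are time (baseline, visit 5, visit 6) and intervention. The covariates for baseline imbalance are age, gender, the two genes and baseline outcome values, including baseline HOMA-IR. Neither insulin use nor diabetes status appears. Sensitivity analyses cover baseline imbalance, outliers, protocol violation and missing data.

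**Baseline sample.** In section 10.1, insulin and glucose are taken at visit 1, where subjects "will arrive after having fasted overnight (10 hours) at 7 to 7:30 am". Section 10.2 lists the same sample at the screening visit, for which no fast or insulin instruction is written.

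**The concern.** HOMA-IR stands for insulin sensitivity only when measured insulin and glucose reflect the subject's own physiology. In someone who injects insulin, two things can go wrong. The assay may count injected insulin, which raises the reading. Injected insulin may also lower glucose and own secretion, which reduces it. The documents name neither the assay nor the insulin products, so the direction cannot be settled from them.

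At stake is the reading of one secondary endpoint in a trial of 20: added noise, some dilution of a true change, and a chance imbalance of users between arms. A decision about users taken after endpoint data have been seen could also look data-driven, because section 19.7 reviews those data once half the patients have completed.

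**Working it through.** The plan gives no HOMA-IR value, SD, assay, number of users or power figure, so there is nothing of its own to reproduce. What follows is illustration.

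**Inputs.** From the documents: 20 subjects (section 5.1) and blocks of 10 with no stratification stated (section 10.1). Assumed: 10 per arm; users falling at random in the enrolment order; HOMA-IR proportional to fasting glucose × fasting insulin; own insulin 15 units; residual injected insulin *r* of 5, 10 or 20 units; a fall *f* of 0, 10% or 30% in both glucose and own insulin. *H* is the user's HOMA-IR without injected insulin.

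**1. Level of one reading.** If the assay detects injected insulin, reading/*H* = (1−f) × [(1−f) × 15 + r] / 15. If it does not, reading/*H* = (1−f)².

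| f | r = 5 | r = 10 | r = 20 | not detected |
|---|---|---|---|---|
| 0 | 1.33 | 1.67 | 2.33 | 1.00 |
| 10% | 1.11 | 1.41 | 2.01 | 0.81 |
| 30% | 0.72 | 0.96 | 1.42 | 0.49 |

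The reading can move either way, from 0.49 to 2.33, with no change in insulin sensitivity.

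**2. Change, which is the endpoint.**
- True fall in own insulin from 15 to 12, with the same residual at each visit: observed change = (1−f)² × (12−15)/15 = −0.20*H*, −0.16*H* and −0.10*H* for f = 0, 10% and 30%. With f = 0 the residual cancels; otherwise the change is diluted.
- No true change, detected residual moving from 10 to 5 units: observed change = (1−f) × (−5)/15 = −0.33*H*, −0.30*H* and −0.23*H*. Divided by 10, one such user moves an arm mean by 0.033*H*, 0.030*H* or 0.023*H*.

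**3. Split of users between arms** (hypergeometric, 10 of 20). P(equal split) is 0.526, 0.418 and 0.372 for 2, 4 and 6 users, so an unequal split has probability 47%, 58% and 63%. Most of these splits are mild: a difference of four or more users has probability 0%, 9% and 14%.

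**4. Precision cost of restricting to non-users.** The SE ratio is √[(1/n₁ + 1/n₂)/0.2], assuming the same spread in users and non-users.
- Equal split: 9+9, 8+8 and 7+7 give 1.05, 1.12 and 1.20.
- All users in one arm: 10+8, 10+6 and 10+4 give 1.06, 1.15 and 1.32. The last needs all six users in one arm: 2 × C(10,6)/C(20,6) = 420/38,760, about 1%.

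**5. When restriction gains precision.** Let *p* be the share of users and *k* the ratio of users' change-SD to that of non-users. With an equal split and degrees of freedom ignored, restriction has the smaller SE when (1−p) + p·k² > 1/(1−p), that is k² > (2−p)/(1−p).
- p = 0.1: k > √(1.9/0.9) = 1.45
- p = 0.2: k > √(1.8/0.8) = 1.50
- p = 0.3: k > √(1.7/0.7) = 1.56

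**The case against.** **The plan already anticipates insulin use.** It has an insulin instruction before each of the three visits, an overnight fast, a fixed arrival time, a stable-medication instruction, and sensitivity analyses for outliers and protocol violation. The medication-pump exclusion in section 6.2 may remove some pump users. Section 8.1 refers to forms ("Please see the screening documents") outside the published text that may record insulin use. All of this limits the problem. But a baseline covariate deals at best with a constant offset, a protocol-violation analysis does not identify a user who followed the instruction, and section 17.1 makes no use of whatever the forms record.

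**The magnitude is assumed, and the widest range concerns level rather than change.** That stands. A constant residual with no fall in glucose or own insulin does no harm to the endpoint, and one drifting user moves an arm mean by only a few hundredths of *H*.

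**Excluding users may cost more than it gains.** That also stands. Unless users' change-SD exceeds that of non-users by the factors in step 5, for which the documents give no evidence, restriction loses precision. Keeping all randomised subjects also keeps the comparison that Aim 2 describes. A reader might infer that non-users must be the main analysis; the documents do not support that.

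**The baseline-visit mismatch is a separate matter.** It is, and it is wider than HOMA-IR: section 10.2 also puts the gene and cognitive measurements at screening, whereas section 10.1 puts them at visit 1. It adds no weight to the insulin-use point.

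**Conclusion.** The point holds as a low-priority weakness in one secondary analysis. Followed as written, section 17.1 puts any insulin users' readings into an endpoint interpreted as insulin sensitivity, although those readings may be high or low for other reasons. The size is unknown: zero if no users enrol, and otherwise dependent on assay, product, timing and number of users, none of which the documents give. Every figure above rests on assumed inputs.

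A reader might go further and infer that the treatment comparison is biased. The documents do not support that: allocation is randomised and blinded, so no bias towards either arm is expected. The expected harm is noise, dilution and chance imbalance. The primary weight endpoint does not use HOMA-IR and is unaffected. Nor does this point show that the insulin instruction itself is wrong.

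**What to change.** **In section 17.1, before the half-way endpoint review in section 19.7:**
- Pre-specify a HOMA-IR analysis restricted to subjects not using insulin at baseline, reported beside the all-randomised analysis. Take insulin use from the screening medical history, so that it is fixed before randomisation.
- Report the number of users per arm.
- Base any statement about insulin sensitivity on the two analyses agreeing.
- The sponsor can choose which is called the main analysis, given the trade-off in step 5. An insulin-use covariate alone would adjust for a mean difference but leave the unreliable readings in.

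**In sections 10.1 and 10.2:** reconcile which visit supplies the baseline insulin and glucose sample, so that baseline HOMA-IR is comparable with visits 5 and 6.

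**Cost.** About two sentences in section 17.1 and one correction to the visit listing. The restricted analysis is less precise, by the factors in step 4; the all-randomised analysis loses nothing. If no users enrol, the two coincide. No change to the insulin instruction is proposed.

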3.0 Background

3.1 Provide the scientific or scholarly background, rationale, and significance of the research based on the existing literature and how it will contribute to existing knowledge. Describe any gaps in current knowledge. Include relevant preliminary findings or prior research by the investigator.

Response:

Transcranial Direct current stimulation (tDCS) is a procedure in which a pair of electrode pads is applied over the scalp to deliver mild direct electric current to a specific area of the brain. It changes spontaneous firing rate of neurons underlying the pads[1], and the persistence of this modification in excitability of neurons can last up to 1 hour after the cessation of electric current[2]. This effect can be prolonged with repetitive stimulation over several consecutive days, most likely mediated by synaptic changes[3].

Left dorsolateral prefrontal cortex is a subregion of the prefrontal cortex considered to be involved in taste[4] and satiation[5]. Previous studies also demonstrated left dorsolateral prefrontal cortex in response to meal is different in lean men and women from obese subjects[6, 7], with obese subjects mounted a more significant response after meal. Therefore, this region of brain is a potential target for obesity intervention.

A recent study showed that tDCS inhibit craving for food[8]. Another prospective study of 9 obese subjects reveal that tDCS is associated with weight loss[9]. Our proposed study will explore the effect of tDCS on weight, appetite and glucose tolerance in long term (over 1 month period) and in a larger study population. We will apply sham tDCS as control. In sham tDCS, the duration of stimulation will be limited to 15 seconds instead of 30 minutes in the active tDCS group. According to previous study, subjects are the not able to differentiate sham from active tDCS [9].

Polymorphism of the catechol-O-methyltransferase (COMT) gene was found to interact with tDCS intervention and change its effect on higher level executive function[10]. The brain derived neurotrophic factor (BDNF) gene polymorphism was also shown to modulate the effect of tDCS on motor cortex plasticity [11]. Therefore, these genes can potentially alter the effect of tDCS on weight, appetite and cognitive response to food.

3.2 Include complete citations or references.

Response:

1. *Wassermann, E.M. and J. Grafman, Recharging cognition with DC brain polarization. Trends Cogn Sci, 2005. 9(11): p. 503-5.*

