11.0 Study Timelines

11.1 *Describe the anticipated duration needed to enroll all study subjects.*

Response: 10 weeks

11.2 *Describe the duration of an individual subject's participation in the study. Include length of study visits, and overall study follow-up time.*

Response: If the subject was found to meet the eligibility criteria, he/she will come to our research center for 6 appointments. Each appointment lasts for 1 hour and the total length of the study is about 2 months

11.3 *Describe the estimated duration for the investigators to complete this study (i.e. all data is collected and all analyses have been completed).*

Response: 18 months

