17.0 Data Management and Analysis

17.1 Describe the data analysis plan, including any statistical procedures. This section applies to both quantitative and qualitative analysis.

Response:

The demographic features of the population and screening lab results will be displayed in tables. Statistical analysis will be conducted using SigmaStat software version 3.1 (SPSS Inc., Chicago, IL). Data will be represented as mean \pm S.E. Sample size cannot be estimated as this is a pilot study. Generalized linear mixed model will be applied to compare the difference in weight, average amplitude of glucose excursion curve, average daily meal count, HOMA-IR, reaction time and percentage correct response in computerized cognitive tests. Predicting variables include time in the study (baseline, visit 5 and visit 6) and type of intervention (active tDCS vs sham). Sensitivity analysis will be performed to evaluate baseline imbalance, outliers, protocol violation, and missing data. The proposed covariants to be evaluated for baseline imbalance includes age, gender, COMT and BDNF gene status, baseline weight, baseline HOMA-IR, baseline average amplitude of glucose excursion curve, baseline average daily meal count, baseline reaction time and percentage correct response.

17.2 If applicable, provide a power analysis.

NOTE: This may not apply to certain types of studies, including chart/records reviews, survey studies, or observational studies. This question is asked to elicit whether the investigator has an adequate sample size to achieve the study objectives and justify a conclusion.

Response: This is a pilot study, so we are not able to estimate sample size. However, previous shorter term study showed a small effect of tDCS on appetite and weight (see reference 9) in nine patients. We consider that by recruiting 20 participants, it will be more likely to detect a significant change, while the total expense will still be within the limit of our fund.

17.3 Describe any procedures that will be used for quality control of collected data.

Response:

Date entered by research staff will be verified by another person independently.

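### Visit 5 cognition is tested after the fifth stimulation with no stated interval, probably within the cited after-effect, yet 17.1 models it as an ordinary time point for a one-month aim

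*Combined protocol and SAP*

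**What the plan says.** Section 10.1 has subjects arrive fasted at Visit 5 and "receive the fifth session of the same intervention. We will then measure body mass index, plasma insulin and glucose, appetite and cognitive function". No minimum interval between stimulation and measurement is given.

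In the active arm subjects "will receive 30 min of anodal tDCS"; in the sham arm they "receive 15 seconds of anodal tDCS" and keep the electrodes on for 30 minutes.

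The background (3.1) states that "the persistence of this modification in excitability of neurons can last up to 1 hour after the cessation of electric current", and adds: "This effect can be prolonged with repetitive stimulation over several consecutive days". Section 11.2 says: "Each appointment lasts for 1 hour and the total length of the study is about 2 months".

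Aim 3 is "To compare change in cognitive performance as a response to food over one month in active tDCS group with sham tDCS group"; Aim 2 sets the same time frame for insulin sensitivity. The analysis plan (17.1) applies a generalized linear mixed model to outcomes that include HOMA-IR, reaction time and accuracy. It says: "Predicting variables include time in the study (baseline, visit 5 and visit 6) and type of intervention (active tDCS vs sham"). It names no interaction between time and intervention, and does not say which visit answers the one-month aims.

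**The concern.** Visit 5 is the only assessment made in a state that one arm has just been put into by the current. Baseline comes before any stimulation: 10.1 describes it ahead of the first session at Visit 1, and 10.2 places it at screening. Visit 6 comes 4 weeks after Visit 5 with no stimulation listed.

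Sham control balances procedure time and fasting, but not the acute effect of the current, which differs between arms by design. A Visit 5 difference in the cognitive task therefore cannot be split into what the last session did and what the course did.

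Two misreadings follow. An intervention effect that draws on Visit 5 would credit a transient state to a one-month objective. A fall from Visit 5 to Visit 6 would look like lost benefit when it might only be the after-effect ending.

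**Working it through.** The plan gives no figure on this point to reproduce. The check has two parts: timing, then what the model returns.

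**Inputs**
- Appointment length: 60 min (11.2).
- Active stimulation: 30 min, with a 30-second ramp at each end (10.1, Visit 1).
- Cognitive task: 20 min (10.1, Visit 1).
- After-effect on excitability: up to 60 min (3.1).
- Visit 6: 4 weeks after Visit 5 (10.1).
- Time levels: baseline, Visit 5, Visit 6; no interaction named (17.1).

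**Timing**
- Time left after stimulation: 60 − 30 = 30 min, or 60 − 30 − 2 × 0.5 = 29 min if the ramps are extra. Electrode set-up shortens it further.
- Time left for everything except the task: 30 − 20 = 10 min, or 29 − 20 = 9 min.
- If the appointment keeps to its stated length, all Visit 5 measures end within about 30 min of the current stopping, inside the 60-min bound.
- For the task to start only after the full window, the visit would have to last 30 + 60 + 20 = 110 min, which is 110 − 60 = 50 min over the stated length.
- Visit 6 is 4 × 7 × 24 = 672 hours after Visit 5, far outside the window.

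**What the model returns**

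Let L be a lasting effect present at Visits 5 and 6, and d an acute effect present at Visit 5 only. The expected differences between arms are:

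| Visit | Active minus sham |
|---|---|
| Baseline | 0 |
| Visit 5 | L + d |
| Visit 6 | L |

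- *As written (time and intervention only).* With balanced, complete data and equal weight on the visits, the intervention term is [0 + (L + d) + L] / 3 = (2L + d) / 3. If L = 0, this is d/3.
- *With the time-by-treatment interaction.* The baseline-to-Visit-6 contrast is L − 0 = L, which is 0 if L = 0. The baseline-to-Visit-5 contrast is L + d and is estimated separately.

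The documents give no value for d. For assumed values with L = 0:

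| Assumed d (SD) | Term as written, d/3 | Baseline-to-Visit-6 contrast |
|---|---|---|
| 0.3 | 0.10 | 0 |
| 0.5 | 0.17 | 0 |
| 0.8 | 0.27 | 0 |
| 1.0 | 0.33 | 0 |

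**The case against.** The strongest reply is that Visit 5 was never the one-month measure. Visit 6 is, and it is free of acute carry-over, so Aims 2 and 3 remain answerable. That stands. The harm arises only if Visit 5 enters the estimate or is read as a lasting effect. Section 17.1 does not rule this out, and read literally it lets Visit 5 in. Its list of predictors is introduced as inclusive, so an interaction may be intended, but none is stated.

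Four further points limit the concern:
- **Timing.** The 1-hour appointment looks nominal, and the order rests on one word with no interval. Hence probably, not certainly, inside the window. An overrun would need to reach 50 minutes before the task started clear of it.
- **Outcomes.** A reader might infer that a Visit 5 difference in HOMA-IR could come entirely from the session just given. The documents do not support this. The 1-hour figure is an upper bound for neuronal excitability, and no acute effect on fasting insulin or glucose is documented. Appetite is measured at the same time, but it belongs to Hypothesis 1 and is not among the outcomes modelled in 17.1.
- **Size.** A reader might put the bias at d/2 by averaging the Visit 5 and Visit 6 changes. The plan specifies no such contrast; its literal model gives about d/3.
- **Reordering.** A reader might infer that measuring before the fifth session would make Visit 5 equivalent to baseline and Visit 6. Section 3.1 says that repeated daily sessions prolong the effect, so a measure about a day after the fourth session is not shown to be free of stimulation. Measuring after the full course is also a recognisable end-of-treatment assessment.

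**Conclusion.** The concern holds for cognition. Visit 5 reaction time and accuracy are probably measured during an acute after-effect that differs by arm, and the model as written would carry about one third of any such effect into the intervention term. That figure assumes balanced, complete data and equal weighting of the three visits; 17.1 states no covariance structure, and other weights would change the fraction. The size of d is unknown.

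For HOMA-IR the same route is possible but undocumented. Weight, the primary endpoint, is unlikely to move within the hour. The continuous glucose monitor endpoints come from recordings of at least 72 hours, which 10.2 assigns to Visits 1 and 6. The trial can still answer Aims 2 and 3 from Visit 6; what is missing is a plan that says so.

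**What to change.** In 17.1:
1. Add the time-by-treatment interaction to the model.
2. Name the between-arm contrast in change from baseline to Visit 6 as the estimate for Aims 2 and 3.
3. Report Visit 5 separately, labelled as an immediate post-stimulation measure, and do not pool it into the one-month estimate.

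This is a text edit with no added visit, procedure or staff. It keeps the measure taken after all five sessions.

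Optionally, if the sponsor wants Visit 5 free of the immediate after-effect, the measures could be taken before the fifth session. The price is that Visit 5 then reflects four completed sessions rather than five. Steps 1 and 2 would still be needed. If the present order is kept, recording the time from the end of stimulation to the start of the task would replace an inferred interval with a known one.
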